2.3.2 Risks

Full details regarding tolerability and safety of Gamunex-C are provided in the prescribing information and the IB. The main risks of Gamunex-C are summarized below:

- Gamunex-C is contraindicated in subjects with a known history of anaphylactic or severe systemic reaction to human immunoglobulins, especially in subjects with antibodies against IgA.

GRIFOLS	Number	BLG-CL-PRT-000020	Version	4.0	Status	Effective	Effective Date	19-Jul-2021
	GC2007 - A Multicenter, Randomized, Open-label Parallel Group Pilot Study to Evaluate Safety and Efficacy of High Dose Intravenous Immune Globulin (IVIG) plus Standard Medical Treatment (SMT) versus SMT alone in Bioscience Industrial Group						Page	25 of 91

- Certain adverse events may be related to the rate of infusion. Subjects must be closely monitored and carefully observed for any symptoms throughout the infusion period.
- There is clinical evidence of an association between IVIG administration and thromboembolic events such as myocardial infarction, cerebral vascular accident (including stroke), PE, and DVT that is assumed to be related to a relative increase in blood viscosity through the high influx of immunoglobulin in at-risk subjects. In subjects at risk for thromboembolic ARs, IVIG products should be administered at the minimum rate of infusion and dose practicable.
- Cases of acute renal failure have been reported in subjects receiving IVIG therapy. In most cases, risk factors have been identified, such as pre-existing renal insufficiency, diabetes mellitus, hypovolemia, overweight, concomitant nephrotoxic medicinal products, or age over 65. In subjects at risk for acute renal failure, IVIG products should be administered at the minimum rate of infusion and dose practicable.
- Aseptic meningitis syndrome (AMS) has been reported to occur in association with IVIG treatment. Discontinuation of IVIG treatment has resulted in remission of AMS within several days without sequelae.
- Gamunex-C may contain blood group antibodies which may act as hemolysins and induce in vivo coating of red blood cells with immunoglobulin, causing a positive direct antiglobulin reaction (Coombs test) and, rarely, hemolysis. Hemolytic anemia can develop subsequent to IVIG therapy due to enhanced red blood cells sequestration. IVIG recipients should be monitored for clinical signs and symptoms of hemolysis. If these are present after IVIG infusion, perform appropriate confirmatory laboratory testing.

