5.3.2 Removal of Subjects

Subjects may withdraw or be withdrawn from the study for the following reasons:

1. At their own request or at the request of their legally acceptable representative.
2. If, in the investigator's opinion, continuation in the study would be detrimental to the subject's well-being.
3. At the specific request of the sponsor.

GRIFOLS Bioscience Industrial Group	Number	BLG-CL-PRT-000020	Version	4.0	Status	Effective	Effective Date	19-Jul-2021	Page	43 of 91
	GC2007 - A Multicenter, Randomized, Open-label Parallel Group Pilot Study to Evaluate Safety and Efficacy of High Dose Intravenous Immune Globulin (IVIG) plus Standard Medical Treatment (SMT) versus SMT alone in									

Also, subjects may be withdrawn for the following reasons:

1. The subject is not able to adhere to the main protocol requirements (major protocol violations).
2. The occurrence of an AE which in the investigator's opinion requires the withdrawal of the subject from the clinical trial.
3. The subject is lost to follow-up.
4. Subject's death.
5. Any event which in the opinion of the investigator impedes the subject's participation in the study.

With regard to individual subject criteria for discontinuation of Gamunex-C IV infusions, discontinuation of study drug treatment will occur if the subject develops any of the following:

- Evidence of hypersensitivity/anaphylaxis to Gamunex-C
- Occurrence of thromboembolic complication (e.g., pulmonary embolism) whether or not related to COVID-19
- Hypertensive emergency with sustained systolic blood pressure > 200 mm Hg unresponsive to intervention or refractory severe hypotension with sustained systolic blood pressure < 90 mm Hg unresponsive to vasopressors
- Development of renal failure with creatinine ≥ 4 mg/dL (or subject becomes dependent on dialysis/renal replacement therapy)

In all cases, the reason for withdrawal must be recorded in the study record and in the subject's records.

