5.3.4 Follow-up of Subjects Withdrawn from Study

For subjects administered any amount of IP (infusion) who discontinue the clinical trial, and for subjects randomized to SMT alone, details for follow-up are delineated below.

For subjects who withdraw from the clinical trial (excluding screen failures), study procedures and assessments scheduled for the Day 15 Visit will be performed at the time of withdrawal, during an unscheduled visit at the time of withdrawal. In addition, to assure major clinical outcomes are adequately captured as a measure of overall safety, these subjects will be asked to return for their chronological Day 29 Clinic Visit (ie, 28 days after Day 1 baseline), unless the unscheduled visit is within 4 days of their chronological Day 29 visit, and provided that they or their legally acceptable representative have not withdrawn consent. At the chronological Day 29 Clinic Visit, all assessments will be performed *except for* central laboratory testing: cytokine panel, respiratory sample for quantitative measurement of SARS-

GRIFOLS Bioscience Industrial Group	Number	BLG-CL-PRT-000020	Version	4.0	Status	Effective	Effective Date	19-Jul-2021	44 of 91
	GC2007 - A Multicenter, Randomized, Open-label Parallel Group Pilot Study to Evaluate Safety and Efficacy of High Dose Intravenous Immune Globulin (IVIG) plus Standard Medical Treatment (SMT) versus SMT alone in								

CoV-2 viral load (obtained via nasopharyngeal swab), and quantitative measurement of IgM and IgG antibodies, which are not required for these subjects at chronological Day 29 for premature withdrawals. These subjects will also have Phone Checks at Day 60 and Day 90 for vital status (living or deceased), and any hospital re-admissions or serious/non-serious adverse events after the Day 29 Final Clinic Visit.

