- Record details of mechanical ventilation parameters (start/end date/time)
- Record oxygen saturation (specify on or off oxygen supplementation)
- Record daily 24-hour fluid balance (intake and output) while in hospital
- Record body weight for assessing fluid balance twice daily on Days 1 through 5 inclusive (at least 8 hours should separate the time from the first recorded weight)

GRIFOLS Bioscience Industrial Group	Number	BLG-CL-PRT-000020	Version	4.0	Status	Effective	Effective Date	19-Jul-2021	Page	51 of 91
	GC2007 - A Multicenter, Randomized, Open-label Parallel Group Pilot Study to Evaluate Safety and Efficacy of High Dose Intravenous Immune Globulin (IVIG) plus Standard Medical Treatment (SMT) versus SMT alone in									

- Record SAEs and TEAEs
- Record standard care concomitant medications

All laboratory tests and serum and plasma samples are required for all study subjects, regardless of treatment assignment. For subjects randomized to IVIG plus SMT all laboratory samples must be obtained prior to the Gamunex-C infusion on the designated day.

On Day 5 ± 1 day the following *additional* assessments will be performed:

- Assessment of ARDS (Berlin Criteria) ([Appendix 3](#))
- SOFA score ([Appendix 4](#))
- Respiratory sample for quantitative measurement of SARS-CoV-2 viral load by NAT or PCR (real-time RT-PCR) (obtained via nasopharyngeal swab)
- Sample for quantitative measurement of IgM and IgG antibodies to SARS-CoV-2 (store serum samples frozen at -70°C for later analysis at an external lab)
- Serum Chemistry (creatinine, albumin, ALT, total bilirubin, LDH)
- Ferritin (serum), D-dimer (plasma, sodium citrate tube), CRP (serum)
- Hematology: absolute lymphocyte count and standard hematology (hemoglobin, hematocrit, platelet count, leukocyte count with differential)
- DAT
- Cytokine panel (IL-1 β , IL-10, IL-6, IL-8, IL-2, interferon γ , and TNF- α). Note: serum samples must be stored at -70°C for later analysis at a reference laboratory.

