### 7.3 Clinical Laboratory Assessments

Clinical laboratory tests will be obtained at the time points presented in Appendix A. Continuous clinical laboratory values will be summarized by presenting descriptive statistics of raw data and change from baseline values at each time point for each treatment group, if feasible. If necessary, quantitative lab values reported in different units for the same lab parameter will be converted to the same units prior to being summarized. Qualitative results at each time point measured will be summarized by presenting the number and percentage of subjects for each category. Shift tables, based on the high/low flags, will also be summarized by treatment group at each visit for all laboratory tests with normal ranges, when available.

Laboratory parameter results from unscheduled visits will be excluded from table summaries but will be included in data listings. When there are repeat scheduled measurements for a given visit, only the last measurement will be used in the table summaries.

Listings will include flags for values outside of the reference ranges, when available, and clinical significance if a laboratory result is deemed abnormal when applicable.

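### SAP 7.3 keeps off-schedule laboratory results out of every laboratory table and plans no worst-value summary, so collected renal and haemolysis values can miss any comparison by arm

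*SAP*

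**What the plan says.** SAP 7.3 summarises laboratory values and changes from baseline at each time point by arm. Three rules decide what reaches those tables.

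- Off-schedule results: "Laboratory parameter results from unscheduled visits will be excluded from table summaries but will be included in data listings".
- Repeats: "When there are repeat scheduled measurements for a given visit, only the last measurement will be used in the table summaries".
- Shifts: "Shift tables, based on the high/low flags, will also be summarized by treatment group at each visit for all laboratory tests with normal ranges".

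SAP section 7 has no summary of the worst post-baseline laboratory value. SAP 4.3 groups data by the nominal visit in the database, so no windowing step brings an excluded value back. SAP 8 applies the Section 7 methods to the interim safety analysis at 50 subjects as well. The excluded results are not discarded: "Listings will include flags for values outside of the reference ranges, when available, and clinical significance if a laboratory result is deemed abnormal when applicable".

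Protocol 7.2.2 to 7.2.7 and Appendix 1 schedule creatinine, bilirubin, LDH, haematology and the direct antiglobulin test on Day 1 and on Days 5, 15 and 29 (each ±1 day). Protocol 7.2.3 adds: "For subjects randomized to IVIG plus SMT all laboratory samples must be obtained prior to the Gamunex-C infusion on the designated day".

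Protocol 2.3.2 says: "Cases of acute renal failure have been reported in subjects receiving IVIG therapy". It also names haemolysis as a risk and asks for confirmatory laboratory tests if signs appear after infusion. One criterion in protocol 5.3.2 for stopping infusions begins "Development of renal failure with creatinine" and sets the threshold at 4 mg/dL or more, or dependence on renal replacement. For subjects who withdraw, protocol 5.3.4 says: "study procedures and assessments scheduled for the Day 15 Visit will be performed at the time of withdrawal, during an unscheduled visit".

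**The concern.** Renal injury and haemolysis are risks the protocol itself attaches to the product, and both show in routine laboratory values. The schedule is sparse, and an unexpected result is likely to come from a sample taken because something looked wrong. Such a sample is often off schedule, and off-schedule results are the ones the tables leave out.

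At stake is the objective, numeric comparison of renal and haematological safety between arms. Listings show individual values but compare nothing. The adverse event tables do compare arms, but each entry depends on an unblinded investigator deciding that a value was clinically important. Protocol section 2 names acute kidney injury as a complication of COVID-19 itself, which makes that judgement harder.

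**Working it through.** The plan gives no figure to reproduce here, and SAP section 7 plans no formal safety tests. The check sets the table rules against the schedule.

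**1. Days covered by a scheduled draw.** From Day 2 to Day 29 there are 28 days and 3 scheduled draws, so 3/28 = 11% of days.

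- Before the first window: it opens on Day 5 − 1 = Day 4, so Days 2 and 3 have no scheduled draw.
- Between the Day 5 and Day 15 draws: 15 − 5 − 1 = 9 days (7 to 11 with the windows).
- Between the Day 15 and Day 29 draws: 29 − 15 − 1 = 13 days (28 − 16 − 1 = 11 to 30 − 14 − 1 = 15).

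**2. Draws relative to dosing.** Infusions run through Day 4 or Day 5, and a draw on an infusion day comes before that day's dose. A Day 5 draw in the 5-day regimen, or a Day 4 draw in either regimen, therefore precedes the last infusion. In those cases the first scheduled value after the full dose is the one at Day 15 ± 1.

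**3. Which collected results fall outside the laboratory tables.**

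- A creatinine on Day 2 or 3 that meets the criterion in protocol 5.3.2: outside every window.
- Confirmatory tests for haemolysis: no scheduled slot.
- The withdrawal laboratory set: the protocol calls that visit unscheduled, so the SAP rule excludes it if read literally. If withdrawal falls within 4 days of chronological Day 29, the Day 29 visit is not requested, and the subject's last laboratory set is then in no laboratory table.
- An earlier repeat at a scheduled visit: replaced by the last one, which may be better or worse.

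**4. How often a short abnormality meets a scheduled draw.** Assume that onset is equally likely on each day of a range and that the abnormality lasts L days. Overlap = (onset days o with o ≤ v ≤ o + L − 1 for some v in {5, 15, 29}) ÷ (all onset days in the range).

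| L (days) | Onset Days 2–14 | Same, with ±1 windows | Onset Days 2–28 |
|---|---|---|---|
| 3 | 5/13 = 38% | 31–46% | 8/27 = 30% |
| 5 | 8/13 = 62% | 46–77% | 13/27 = 48% |
| 7 | 10/13 = 77% | 62–92% | 17/27 = 63% |
| 10 | 13/13 = 100% | 85–100% | 23/27 = 85% |

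The table describes the sampling schedule and not the effect of the SAP rule. An abnormality between draws is lost through the rule only if blood was taken and the result entered in the database. The documents do not say how often that happens, so the share of episodes lost through the rule could lie anywhere from zero to the whole share that misses a draw.

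**The case against.** The strongest reply is that restricting by-visit tables to scheduled visits is sound practice. It keeps time points comparable between arms, and in an open-label trial off-schedule sampling may differ by arm. That stands, and it is why the by-visit tables should stay as planned.

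A second reply is that serious abnormalities are not invisible. Protocol 8.3.8 says a laboratory abnormality that needs treatment, causes clinical manifestations, leads to withdrawal or is judged clinically significant should be reported as an adverse event. SAP 7.2.5 tabulates such events by term, severity, Grade 3 or higher, relatedness and seriousness. A creatinine that stops the infusions would be expected to take this route. Scheduled creatinine, haemoglobin, bilirubin, LDH and the direct antiglobulin test are tabulated in both arms. This also stands. What remains is that the adverse event route rests on unblinded judgement and that scheduled values need not include the worst one.

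Several stronger readings are tempting, and the documents do not support them.

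- That many values are lost: no count of unscheduled or repeat results is given, and nothing says that routine ICU values from other days enter the CRF.
- That 70%, 52% and 37% of episodes lasting 3, 5 and 7 days (100% minus the last column above) reach no table: those shares are gaps in sampling under an assumed onset, and they ignore the adverse event tables.
- That every withdrawn subject's safety laboratory data disappear: scheduled draws before withdrawal remain. Protocol 5.3.4 also asks these subjects back for Day 29 with local chemistry and haematology, unless withdrawal is within 4 days of that visit or consent is withdrawn. Nor do the documents show how the withdrawal visit is labelled in the database.
- That stopping infusions for creatinine removes a subject from later draws: protocol 5.3.2 treats stopping the infusions separately from leaving the study.
- That the last-of-repeats rule systematically favours recovered values: the last value can be worse.

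**Conclusion.** The gap is real and modest. Under SAP 7.3 as written, a collected off-schedule creatinine or haemoglobin result enters no laboratory table by arm, and no worst-value summary makes up for this. The same holds for confirmatory haemolysis tests and, on a literal reading, for the withdrawal laboratory set. The rules apply to both arms, so no direction of bias can be claimed.

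The number of values affected cannot be derived from the documents. The overlap figures show only that short abnormalities can fall between scheduled draws while long ones are mostly caught. They rest on assumed onset and duration. The conclusion also assumes that some off-schedule results are collected, which the SAP anticipates by planning to list them. The primary endpoint, sample size and significance level are untouched. The change is worth making because it is cheap and the risks concerned are named in the protocol.

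**What to change.** Keep the by-visit tables, including the last-of-repeats rule, as planned. Putting the worst repeat into by-visit summaries is not advised, because it would mix selected extremes, and possibly erroneous first results, into the means. Add to SAP 7.3:

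- By arm in the Safety population, the worst post-baseline value through Day 29, covering at least maximum creatinine, bilirubin and LDH and minimum haemoglobin and platelets. Use all collected scheduled, repeat, unscheduled and withdrawal-visit results.
- By arm, a baseline-to-worst shift table for the same parameters and results.
- The analysis visit to which the withdrawal laboratory set is assigned, fixed before database lock.
- The number of samples per subject by arm, shown with the worst-value table. More frequent sampling alone makes an extreme value more likely to be found, and open-label care may produce unequal sampling.

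The cost is SAP wording, the two tables with their sample counts, and one mapping rule. The tables use whatever has been collected and listed. They require no extra blood draws, and they cannot recover values that were never entered.

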#### **7.4 Vital Signs**

Descriptive summaries of the vital signs (both raw and change from baseline values) including systolic and diastolic blood pressure, pulse, respiratory rate, and body temperature will be prepared for each treatment group by visit.

Qualitative results at each time point measured, including severe dehydration (no/yes), sternal capillary refill time >2 seconds (no/yes/unknown), and clinically significant (no/yes), will be summarized by presenting the number and percentage of subjects for each category.

For Gamunex-C plus SMT group, vital signs will also be collected within 1 hour prior to the start of Gamunex-C infusion, 30 minutes after the start of infusion, and hourly through the end of Gamunex-C infusion. The raw data and change from baseline values, as well as whether clinically significant at each time point will be summarized for the Gamunex-C plus SMT group only.

Unscheduled visits will be excluded from the summaries but will be included in the data listings.

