An infusion may be stopped at the discretion of the medical personnel according to normal practice, for instance if there is extravasation at the IV site, and then restarted using a new IV site. However, if a hypersensitivity reaction occurs, such as anaphylaxis, the infusion of IV Gamunex-C will be stopped permanently, and no further Gamunex-C infusions will be given. During infusion vital signs will be measured and the patient carefully observed. Early signs and symptoms of hypersensitivity reactions may include pruritus; generalized urticaria; flushing; swollen lips, tongue, or uvula; wheezing; tightness of the chest; dyspnea; hypotension; and syncope. If hypersensitivity symptoms occur, promptly stop study drug infusion and begin appropriate therapy. Such patients who discontinue infusion will be monitored according to standard of care until hypersensitivity/anaphylaxis resolves and will not receive any further IP.

Additionally, if there is a high clinical suspicion of fluid overload the infusion of Gamunex-C should be slowed or stopped. If Gamunex-C is stopped, the Principal Investigator should consider restarting Gamunex-C infusion when clinical signs of fluid overload have resolved, or the patient has shown adequate response to therapy.

Furthermore, vital signs will be measured within 1 hour prior to the start of Gamunex-C infusion, 30 minutes after the start of infusion, and hourly through the end of Gamunex-C infusion. If the systolic blood pressure measured within 1 hour prior to the start of Gamunex-C infusion is > 160 mm Hg, then measures to lower blood pressure below this threshold should be administered and documented prior to commencing Gamunex-C infusion. To commence the Gamunex-C infusion, the systolic blood pressure must be < 160 mm Hg.

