7.2.2 Screening/Baseline and Randomized Treatment (Day 1)

All required screening and baseline (pre-infusion Day 1) procedures/assessments will be performed prior to administration of the IP (for subjects randomized to the combination arm).

Assessments include the following:

- Informed consent
- Inclusion/exclusion criteria
- Pregnancy test for females of child-bearing potential
- Record demography (age [year of birth], age at screening [years], gender [if female, fertility status], race, and ethnicity), disease characteristics (date of exposure, date of onset)
- Ordinal Scale assessment
- National Early Warning Score (NEWS) ([Appendix 2](#))

GRIFOLS Bioscience Industrial Group	Number	BLG-CL-PRT-000020	Version	4.0	Status	Effective	Effective Date	19-Jul-2021	49 of 91
	GC2007 - A Multicenter, Randomized, Open-label Parallel Group Pilot Study to Evaluate Safety and Efficacy of High Dose Intravenous Immune Globulin (IVIG) plus Standard Medical Treatment (SMT) versus SMT alone in								

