After all Screen/Baseline assessments are complete subjects may be randomized.

Subjects in the combination arm may receive the first infusion of Gamunex-C on Screen/Baseline and Randomized Treatment visit (Day 1) if eligibility criteria are met, and all pre-infusion assessments are performed. Subjects in the combination arm will receive a total of 2 g/kg Gamunex-C in divided doses. At the prerogative of the Principal Investigator the 2 g/kg dose may be divided into 4 days (500 mg/kg/day) or 5 consecutive days (400 mg/kg/day).

Vital signs will be monitored during Gamunex-C infusion. Vital signs will be measured within 1 hour prior to the start of Gamunex-C infusion, 30 minutes after the start of infusion, and hourly through the end of Gamunex-C infusion. If the systolic blood pressure measured within 1 hour prior to the start of Gamunex-C infusion is > 160 mm Hg, then measures to lower blood pressure below this threshold should be administered and documented prior to commencing Gamunex-C infusion. To commence the Gamunex-C infusion, the systolic blood pressure must be < 160 mm Hg.

7.2.3 SMT, Randomized IVIG Treatment, Daily Evaluations (Days 2 through 10 inclusive) and Additional Day 5±1 Day Assessments

All subjects receive continued SMT. Subjects randomized to IVIG plus SMT will receive the remainder of the net 2 g/kg dose in divided doses at the Principal Investigator's prerogative on consecutive days through Day 4 (500 mg/kg/day) or through Day 5 (400 mg/kg/day) to achieve the total dose of 2 g/kg body weight. Subjects receiving Gamunex-C infusions will have vital signs measured within 1 hour prior to the start of each Gamunex-C infusion, 30 minutes after the start of infusion, and hourly through the end of Gamunex-C infusion. If the systolic blood pressure measured within 1 hour prior to the start of Gamunex-C infusion is > 160 mm Hg, then measures to lower blood pressure below this threshold should be administered and documented prior to commencing Gamunex-C infusion. To commence the Gamunex-C infusion, the systolic blood pressure must be < 160 mm Hg.

Daily assessments include the following:

- Ordinal Scale assessment
- NEWS ([Appendix 2](#))
- Clinical features key symptoms: fever, cough, shortness of breath, fatigue, myalgia etc.
- Vital signs (temperature, systolic and diastolic blood pressure, pulse, respiratory rate)
- Record any supplemental oxygen administration (type, %, flow start/end date/time)

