#### 4.6 Data Derivations and Transformations

The following derivations will be used in this study:

Study Day:

- Date of assessment – date of randomization + 1 for assessments done on or after date of randomization
- Date of assessment – date of randomization for assessments done before date of randomization

Baseline Observation: the last non-missing value prior to randomization.

Duration:

- Duration in days = end date – start date + 1
- Duration in minutes = end time in minutes – start time in minutes

Origin or Start Date for Time to Event Endpoints:

- Time to death: date of randomization
- Time to ICU Discharge (actual and medical equivalence, if applicable): date of randomization or date of ICU admission, whichever was later
- Time to Hospital Discharge (actual and medical equivalence, if applicable): date of randomization
- Time to Clinical Response: date of randomization

Event Date for Time to Clinical Response:

- If a subject met the criteria for clinical response at multiple assessments, the date of the first assessment meeting the definition of clinical response will be used as the event date for deriving time to clinical response.

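### Vital signs during infusion are summarised as change from the pre-randomisation baseline, which mixes within-infusion change with earlier drift and can reverse its sign in individual subjects

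*SAP*

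**What the plan says.** SAP 4.6 opens with "The following derivations will be used in this study" and gives one baseline: "Baseline Observation: the last non-missing value prior to randomization". It makes no exception for infusion data.

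SAP 7.4 plans two sets of vital-sign summaries. The first is by visit, in both arms. The second is for the Gamunex-C arm only, where "vital signs will also be collected within 1 hour prior to the start of Gamunex-C infusion, 30 minutes after the start of infusion", and then hourly until the infusion ends. For this second set, "The raw data and change from baseline values, as well as whether clinically significant at each time point will be summarized". No reference specific to an infusion is named, so the value taken before the infusion is one more time point compared with baseline.

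Protocol 7.2.2 fixes the order on Day 1: "After all Screen/Baseline assessments are complete subjects may be randomized", with the first infusion after that. Protocol 7.2.3 places the remaining infusions on consecutive days through Day 4 or Day 5. Protocol 6.1 adds that if systolic pressure in the hour before an infusion is above 160 mm Hg, "measures to lower blood pressure below this threshold should be administered and documented prior to commencing Gamunex-C infusion", and that the infusion may begin only below 160. Exclusion criterion 14 bars hypertensive subjects only above 200 mm Hg at Screening.

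SAP 8 applies the Section 7 methods, naming 7.4, to the safety interim after 50 subjects.

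**The concern.** Readings this frequent are useful for showing how a subject responds while the product is running. Protocol 4.4.1.1 asks for careful observation for acute reactions, and Protocol 2.2 and 8.3.1 name a fall in blood pressure among the known risks. The natural comparison is with the subject's state just before that infusion.

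The plan compares with a value from before randomisation instead. For every infusion after the first, that value is at least a day old in a patient receiving ICU-level care. For a subject who was hypertensive at baseline, the protocol itself requires the pressure to be brought down between the reference and the infusion. A table built this way can show a small rise for a subject whose pressure fell sharply, or a fall for one whose pressure rose. Reviewers at the interim would see the same table.

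**Working it through.** The documents give no figure to reproduce on this point and no blood pressure distribution, so the check is algebra plus labelled illustrations.

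**Notation.** B is the baseline before randomisation (SAP 4.6), P is the last value before the infusion starts, and X is a value during the infusion.

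**Identity.** X - B = (X - P) + (P - B). The planned change equals the within-infusion change plus the prior drift. Its sign is opposite to X - P whenever P - B has the opposite sign to X - P and is larger in size.

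**Age of the reference.** With randomisation on Day 1 and infusion k on Day k, B is about k - 1 days old. That is 1 to 3 days for infusions 2 to 4 and 4 days for infusion 5. So 3 of 4 or 4 of 5 infusions use a reference at least about a day old.

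**Drift built in by the protocol.** If B is above 160, then P must be below 160 and P - B is negative by more than B - 160. For B = 190 the drift is below -30, so any X under 190 is reported as a fall, even if the pressure rose by 30 during the infusion.

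**Single-subject illustrations (mm Hg, constructed).**

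| B | P | X | Planned: X - B | Within infusion: X - P |
|---|---|---|---|---|
| 190 | 150 | 175 | -15 | +25 |
| 170 | 150 | 160 | -10 | +10 |
| 100 | 135 | 105 | +5 | -30 |

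**How often signs might disagree.** Assume X - P has mean +10 and SD 10, independent of P - B. Simulated results:

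| Mean drift | Mean of X - B | Share of subjects with opposite sign, drift SD 10 / 15 / 20 |
|---|---|---|
| 0 | +10 | 18% / 25% / 30% |
| -10 | 0 | 37% / 39% / 41% |
| -20 | -10 | 60% / 57% / 55% |

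The SD of the change rises from 10 to √(10² + 10²) = 14.1, √(10² + 15²) = 18.0 or √(10² + 20²) = 22.4.

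**What can be recovered.** If the same subjects contribute at both times, mean(X - B) - mean(P - B) = mean(X) - mean(P) = mean(X - P). In a simulated set of 50, all three came to 10.27. The SD of X - P needs the covariance of X and P, which the planned tables do not give. They also do not give the largest individual changes or the number of subjects beyond a threshold.

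**Late time points.** Following the protocol's rate steps (0.5 mg/kg/min for 30 minutes, then doubling every 15 or 30 minutes to 4):
- 400 mg/kg: 60 + (400 - 60)/4 = 145 min, or 90 + (400 - 105)/4 = 163.75 min.
- 500 mg/kg: 60 + (500 - 60)/4 = 170 min, or 90 + (500 - 105)/4 = 188.75 min.
- At the starting rate throughout: 400/0.5 = 800 min, or 500/0.5 = 1,000 min.

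After the first two or three hours, increasingly only the slower infusions contribute, and even the mean within-infusion change can no longer be read from the tables.

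**The case against.** A reader might infer that the change during infusion is not measured at all. The documents do not support that. Raw values before and during infusion are summarised, together with clinical significance at each time point, and subject data are listed (SAP 4).

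A reader might also infer that infusion reactions would be missed. Nor does that follow. Intolerance at any rate is recorded as an adverse event (Protocol 2.4.1), the rate and timing of events during infusion are captured (Protocol 8.3.8), listings flag such events (SAP 7.2.5), and dose interruptions are summarised (SAP 7.1). The numeric stopping criteria in Protocol 8.5 rest on deaths and adverse events, not on this table. Vital signs are not a listed safety endpoint, and SAP 7 plans no formal safety testing.

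A third inference is that a pre-infusion reference would isolate the effect of IVIG. It would not: the control arm has no matching readings, and a recent measure to lower blood pressure would still act during the infusion.

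For the first infusion the gap may be small. Protocol 7.2.2 describes baseline as pre-infusion on Day 1 ("All required screening and baseline (pre-infusion Day 1) procedures/assessments will be performed prior to administration of the IP"), and no passage says that the reading within the hour must follow randomisation. A programmer might also choose the pre-infusion value unprompted, but SAP 4.6 does not tell them to.

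All of this limits the consequence. It does not supply the missing within-subject summaries.

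**Conclusion.** The point holds as a weakness in a descriptive safety summary. Followed as written, the SAP reports a change that combines within-infusion change with earlier drift. For individual subjects the sign can be wrong, by 40 mm Hg in the most extreme illustration (+25 against -15). For subjects with baseline systolic pressure above 160 mm Hg, the direction of the distortion follows from the protocol's own rule. For others it depends on drift that the documents do not quantify.

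The simulated shares rest on assumed means, SDs and independence. They show a range, not an expectation. The documents do not show that a summary mean would reverse: with zero mean drift it does not shift at all. No endpoint, test or numeric stopping rule depends on the table. What is lost is the within-subject spread, the extremes, the count of subjects with a given rise or fall, and the mean itself at late time points. A change is worth making because the measurements are already required.

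**What to change.** In SAP 7.4, define the reference for the infusion vital signs as the last value recorded before the start of that infusion, after any measure to lower blood pressure. The words after any measure matter: the first reading within the hour can be the one that triggers the lowering, and using it would reproduce the problem.

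Summarise change from this reference by infusion number and time point, showing n at each. Add each subject's maximum rise and maximum fall in systolic pressure and pulse. Label the output as within-subject change during infusion. Keep change from the study baseline for the by-visit tables and, if wanted, as a secondary infusion display. Use the same layout at the 50-subject interim.

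The cost is a few more descriptive tables, each double programmed under SAP 4.1. One thing to confirm is that the reading showing pressure below 160 mm Hg after lowering is entered in the eCRF. The protocol implies that it is taken, but the documents do not say where it is recorded.
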